6.3 Primary Study Phase

6.3.1 AEC peak (Visit 3)

Subjects will return to the clinic at the predicted AEC peak (denoted by * in [Figure 1](#)) as determined by their individual history of EAE cycle times. For a 4-week EAE cycle time, Visit 3 would occur at about Day 7 (± 3 days). For subjects whose ANC peak and AEC peak are closer together than a week, Visits 2 and 3 may be combined.

The following procedures and laboratory tests will be performed:

- Targeted history and physical examination, including limb measurements
- Vital signs, including weight
- Review of symptom/weight logs and patient-reported outcome measures adherence

- CBC with differential
- Routine laboratory testing, including acute care, hepatic, and mineral panels, LDH, CPK, CRP, and urinalysis
- Serum tryptase, aldolase, and quantitative immunoglobulin levels (including IgE)
- Collection of serum or plasma and urine for immunologic analyses and quantification of eosinophil granule proteins
- Collection of whole blood for storage of plasma and cells for research studies
- Whole blood lymphocyte phenotyping (TBNK) and RNAseq
- Optional skin punch biopsy, if not done at Visits 1 or 2
- AE assessment

6.3.2 AEC nadir and mepolizumab administration (Visit 4)

Visit 4 will be scheduled to capture the AEC nadir. We anticipate that, for most subjects (assuming a 4-week cycle time), this will fall at about Day 15 (± 3 days). The schedule may be adjusted based on results of at-home CBCs.

The following procedures and laboratory tests will be performed:

- Targeted history and physical examination, including limb measurements
- Vital signs, including weight
- Review of symptom/weight logs and patient-reported outcome measures adherence
- CBC with differential
- Routine laboratory testing, including acute care panel, hepatic panel, mineral panel, LDH, CPK, CRP, and urinalysis
- Urine pregnancy test (females of childbearing potential only)
- Serum tryptase, aldolase, and quantitative immunoglobulin levels (including IgE)
- Collection of serum or plasma and urine for immunologic analyses and quantification of eosinophil granule proteins
- Collection of whole blood for storage of plasma and cells for research studies
- Whole blood lymphocyte phenotyping (TBNK) and RNAseq
- AE assessment

Following completion of the evaluations and pregnancy test (if applicable), mepolizumab 700 mg IV will be administered in the 5SW Day Hospital. The drug will be infused over about 30 minutes. Vitals will be checked and subjects will be able to leave 30 minutes after the infusion.

6.3.3 Predicted ANC peak (Visit 5)

Visit 5 will be scheduled based on the individual subject's cycle length to coincide with the predicted ANC peak. It is possible that mepolizumab administration may alter cycle times, which could affect the scheduling of this visit; however, the time between each infusion will be about 1 month. Every effort will be made to schedule Visit 5 in advance of Visit 6; in the event that Visit 5 occurs within 1 day of Visit 6, only collection of whole blood for storage will be performed for Visit 5.

The following procedures and laboratory tests will be performed:

- Targeted history and physical examination, including limb measurements
- Vital signs, including weight
- Photography (with infrared thermography if available)
- Review of symptom/weight logs and patient-reported outcome measures adherence
- CBC with differential
- Routine laboratory testing, including acute care panel, hepatic panel, mineral panel, LDH, CPK, CRP, and urinalysis
- Serum tryptase, aldolase, and quantitative immunoglobulin levels (including IgE)
- Collection of serum or plasma and urine for immunologic analyses and quantification of eosinophil granule proteins
- Collection of whole blood for storage of plasma and cells for research studies
- Whole blood lymphocyte phenotyping (TBNK) and RNAseq
- AE assessment

In order to capture the peak AEC post-mepolizumab (denoted by ** during blood draws in [Figure 1](#)), subjects will continue 2-3X/week blood draws for CBC with differential until Visit 6. Additionally, at the time of the predicted peak AEC, urine and blood will be collected for shipment to the NIH.

6.3.4 Mepolizumab administration (Visit 6)

Visit 6 will be scheduled 28 days (\pm 5 days) after Visit 4.

The following procedures and laboratory tests will be performed:

- Targeted history and physical examination, including limb measurements
- Vital signs, including weight
- Review of symptom/weight logs and patient-reported outcome measures adherence
- CBC with differential
- Routine laboratory testing, including acute care panel, hepatic panel, mineral panel, LDH, CPK, CRP, and urinalysis
- Urine pregnancy test (females of childbearing potential only)
- Serum tryptase, aldolase, and quantitative immunoglobulin levels (including IgE)
- Serum or plasma and urine for eosinophil granule protein and mediator levels
- Collection of whole blood for purification and storage for research studies
- AE assessment

Following completion of the evaluations and pregnancy testing (if applicable), mepolizumab 700 mg IV will be administered in the Day Hospital.

There will not be additional at-home blood or urine collections under this protocol after Visit 6.

6.3.5 Mepolizumab administration (Visit 7)

Visit 7 will be scheduled for 28 days (± 5 days) after Visit 6. The following procedures and laboratory tests will be performed:

- Targeted history and physical examination, including limb measurements
- Vital signs, including weight
- Review of monthly patient-reported outcome measures adherence
- CBC with differential
- Routine laboratory testing, including acute care panel, hepatic panel, mineral panel, LDH, CPK, CRP, and urinalysis
- Urine pregnancy test (females of childbearing potential only)
- Serum tryptase, aldolase, and quantitative immunoglobulin levels (including IgE)
- AE assessment

Following completion of the evaluation and pregnancy testing (if applicable), mepolizumab 700 mg IV will be administered in the Day Hospital.

6.3.6 Completion of primary and secondary endpoint assessments (Visit 8)

Visit 8 will again be scheduled 28 days (± 7 days) after Visit 7. This visit may occur over several days.

The following procedures and laboratory tests will be performed:

- Targeted history and physical examination, including limb measurements
- Vital signs, including weight
- CBC with differential
- Routine laboratory testing, including acute care, hepatic, and mineral panels, CRP, and urinalysis
- Serum tryptase, aldolase, and quantitative immunoglobulin levels (including IgE)
- Collection of serum or plasma and urine for immunologic analyses and quantification of eosinophil granule proteins
- Collection of whole blood for isolation and storage of plasma and cells for research studies
- Whole blood lymphocyte phenotyping (TBNK) and RNAseq
- Optional bone marrow biopsy and aspiration, requested of subjects for whom a sample was collected/available prior to study treatment (may be done once at any time while on study drug)
- AE assessment

After completion of the procedures described above, subjects who have received benefit from mepolizumab administration will begin the Dose De-escalation Phase (Visits 8-14, as outlined in section [6.4](#)).

For subjects who do not participate in the Dose De-escalation Phase, Visit 8 will be the end of study visit.

6.4 Dose De-escalation Phase

6.4.1 Initiation of de-escalation (Visit 8)

For subjects who demonstrated clinical benefit from mepolizumab administration, Visit 8 will begin the Dose De-escalation Phase. The following additional procedures and laboratory tests will be performed:

- Urine pregnancy test (females of childbearing potential only)
- Teaching for autoinjector drug administration (if applicable)

Following completion of these procedures, mepolizumab 500 mg IV will be administered in the Day Hospital. The drug will be infused over about 30 minutes. Vitals will be checked and subjects will be able to leave 30 minutes after the infusion.

The subjects will start a log of symptoms of EAE that they will fill out weekly (rather than daily) to track symptoms and weight during de-escalation. They will also continue patient-reported outcome measures: weekly for angioedema symptoms and monthly for quality of life. These logs and measures will be completed electronically using REDCap (section 7.1.3). Subjects will complete the logs and measures through the end of the De-escalation Phase (Visit 14).

If subjects experience a symptomatic flare between visits at any time during the dose de-escalation phase, they may be requested to obtain additional bloodwork for safety reasons.

6.4.2 Mepolizumab administration at 500 mg (Visits 9 and 10)

Visits 9 and 10 will be scheduled 28 days (± 7 days) from the prior visit. In-person visits are preferred, but these visits may be performed remotely if needed due to COVID-19 restrictions and difficulties with travel. In such cases, the pharmacy will provide autoinjectors for SC administration. Visit 10 should be performed at NIH if feasible.

The following procedures and laboratory tests will be performed:

- Targeted history and physical examination, including limb measurements. If the visit is conducted remotely, a targeted history and physical examination will be conducted virtually.
- Vital signs, including weight. The subject will measure and report their weight and temperature if the visit is performed remotely.
- Pregnancy test (females of childbearing potential; not performed at a remote visit)
- Review of symptom/weight logs and patient-reported outcome measures adherence

- CBC with differential
- Collection of serum or plasma and urine for immunologic analyses and quantification of eosinophil granule proteins (not performed at a remote visit)
- AE assessment
- Visit 10 only:
 - Routine laboratory testing, including acute care, hepatic, and mineral panels, LDH, CPK, CRP, and urinalysis (not performed at a remote visit)
 - Serum tryptase, and aldolase, serum immunoglobulins and IgE
 - Collection of whole blood for isolation and storage of plasma and cells for research studies (not performed at a remote visit)
 - Whole blood lymphocyte phenotyping (TBNK) (not performed at a remote visit) and RNAseq

Following completion of the evaluation and pregnancy testing (if applicable), mepolizumab 500 mg will be administered by IV infusion or by SC injection.

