Females with reproductive potential must either practice complete and uninterrupted abstinence from heterosexual activity or use 2 of the following methods of contraception with their partners. The 2 methods must include either 2 barrier methods, or 1 barrier method and 1 non-barrier method, both of which must be consistently used:

Barrier Methods:

- 1) Diaphragm with spermicide
- 2) Cervical cap with spermicide or contraceptive sponge (for nulliparous subjects only)
- 3) Male or female condom (cannot be used together)

Non-Barrier Methods

- 1) An intrauterine device with a documented failure rate of <1%

- 2) Hormonal contraception: pill (estrogen/progestin or progestin-only), patch, vaginal ring, rod implanted in the skin, or subcutaneous injection methods

Females of childbearing-potential must have a negative pregnancy test result prior to receiving mepolizumab at each on-site study visit. During the course of the study, if a woman becomes pregnant or suspects she is pregnant, she should inform the study staff and her primary care physician immediately. Subjects who become pregnant will be entered into the mepolizumab pregnancy registry.

Fertility: There is no fertility data in humans. Animal studies showed no adverse effects of anti-IL-5 treatment on fertility.

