4.5 Justification for Exclusion of Women, Minorities, Children, and Special Populations

Exclusion of Women:

- **Pregnancy:** Pregnant women are excluded from this study because the effects of mepolizumab on the developing human fetus are unknown (see section 4.3).

- **Breastfeeding:** Mepolizumab was excreted into the milk of cynomolgus monkeys at concentrations that were less than 0.5% of those detected in plasma. Because of the unknown but potential risk for adverse events (AEs) in nursing infants secondary to treatment of the mother with mepolizumab, subjects who are breastfeeding are not eligible for enrollment.

Exclusion of Children:

Although mepolizumab is approved for use in children 6 years and older with severe asthma and 12 years and older in HES, there is insufficient data in children with EAE to judge the potential risks. Moreover, the amount of blood required by this study exceeds the volume permitted for children; therefore, children are excluded from this study.

Exclusion of Decisionally Impaired Adults:

Adults who lack decision-making capacity to consent are not eligible for enrollment in this study (section 4.3), and an enrolled subject who permanently loses decision-making capacity to consent during the study will be withdrawn (section 12.8). NIH Policy 403 *Research with Subjects Lacking Capacity to Consent* will be followed.

5. Study Agent/Interventions

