For the SC formulation: Mepolizumab administration will occur via an autoinjector and will be given by the subject or a caregiver as multiple injections of 100-mg each. Each injection should be given into the thigh or abdomen (avoiding the 5 cm [2 inches] around the navel) when given by the subject or caregiver; the upper arm may be used if the injection is administered by a caregiver. Each injection site should be separated by at least 5 cm (2 inches). Injections should not be administered into areas of skin that are tender, bruised, red, or hard. If a dose is missed, it should be administered as soon as possible. Thereafter, the subject should resume dosing on the usual day of administration. If the next dose is already due, then it should be administered as planned.

Dose Adjustments/Modifications/Delays

During the Primary Study Phase administering mepolizumab at 700 mg IV, the dose will remain the same without modification unless held or stopped due to a

pause (section 12.5), halt (section 12.6), or withdrawal of the subject (section 12.8). During the Dose De-escalation Phase, the dose will be reduced as outlined in the protocol unless held or stopped due to a pause, halt, or withdrawal of the subject.

Duration of Therapy

A total of 3 doses of 700 mg IV will be given on this protocol over a 3-month duration for all subjects; subjects in the Dose De-escalation Phase will have 6 months of additional de-escalating doses at 500 mg (3 doses) and 300 mg (3 doses). The total duration of therapy for participation in both the Primary Study Phase and the Dose De-escalation Phase will be 9 months.

Tracking of Dose

A record of the number of doses and lots used will be kept in the pharmacy for doses administered in-person at the NIH Clinical Center Day Hospital. For remote visits during the Dose De-escalation Phase, subjects will either have an observed administration via telehealth or will log the dose on a dose tracker.

Limitations on Prior Therapy

Subjects who have received mepolizumab within 6 months or 5 half-lives (whichever is longer) will not be eligible for this protocol.

Use of Ancillary Medications/Over-the-Counter Products/Foods

Only corticosteroids will be permitted for treatment in addition to mepolizumab. There are no restrictions on use of other prescribed medications, over-the-counter products or foods.

Subject Access to Study Agent After End of Study Assessments

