5.6 Prohibited Medications and Procedures

Treatment with other biologics or immunosuppressive or cytotoxic agents will not be permitted unless discussed with and approved by the investigator.

6. Study Schedule

All study assessments/procedures required for each study visit are summarized in Appendix B: Schedule of Procedures/Evaluations. Windows for the study timepoints are specified where appropriate. Blood volumes are given in [Appendix C: Blood Volumes for Specimen Collection](#). Research studies are detailed in [Appendix H: Research Studies](#).

If in-person study visits are limited due to the COVID-19 pandemic, study visits may be rescheduled or study procedures may be modified to allow for continued safety monitoring and data collection for study endpoints remotely. If a visit needs to be rescheduled as a remote visit, a member of the study team will contact subjects with sufficient time prior to the study timepoint to make arrangements. In-person visits may be replaced with or modified to include phone calls, virtual telehealth visits or visits with a local healthcare provider for assessment and sample collection. Mandatory study procedures to be performed at remote visits are indicated for applicable visits throughout section 6. For example, EAE symptom logs can be completed electronically, and blood and/or urine samples may be collected with a local specialist or healthcare provider and sent in for clinical and research analyses. However, some research blood cannot be shipped and would be waived based on the discretion of the principal investigator. Regular phone or virtual calls will occur (as per the assessment schedule or more frequently if needed) for safety monitoring and discussion of the subject's health status until the subject can again visit the site.

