12.3 Pregnancy

Although pregnancy itself is not an AE, events occurring during pregnancy, delivery, or in the neonate (e.g., congenital anomaly/birth defect) may be AEs or serious AEs (SAEs).

In the event of pregnancy, the following steps will be taken:

- Discontinue the study agent and procedures and withdraw from this study, but continue to follow-up for safety until delivery or termination of the pregnancy on 94-I-0079.
- Enroll in pregnancy registry.
- Report to the IRB.
- Advise research participant to notify the obstetrician of study participation and study agent exposure.

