Clinical assessments and laboratory evaluations									
Targeted medical history and physical examination	X	X	X	X	X	X	X	X	X
Limb measurements[^]	X	X	X	X	X	X	X	X	X
Vital signs including weight[^]	X	X	X	X	X	X	X	X	X
Symptom log and PROs[#]	X	X	X	X	X	X	X	X	X
Autoinjector training (for remote subjects)	X								
Mepolizumab	X	X	X	X	X	X			
CBC with differential		X	X	X	X	X	X	X	X
Hepatic panel			X				X		
Mineral panel			X				X		
LDH, CPK				X				X	
C-reactive protein				X				X	X
Urinalysis				X				X	X

Serum tryptase		X				X	X
Serum aldolase		X				X	X
Serum immunoglobulins	X					X	X
Serum IgE levels	X					X	X
Urine pregnancy test*	(X)						
Research laboratory studies							
Eosinophil and PBMC purification from whole blood and storage		X				X	
Urine for eosinophil granule protein and mediator levels	X	X				X	
Whole blood flow for TBNK cell subsets and RNAseq		X				X	
Serum or plasma for eosinophil granule protein and mediator levels	X	X				X	
Study assessments							
AE assessments	X	X	X	X	X	X	X

Key: AE- adverse event; CBC- complete blood count; CPK- creatine kinase; IgE- immunoglobulin E; LDH- lactate dehydrogenase; PBMC- peripheral blood mononuclear cell; PROs- patient-reported outcome measures; TBNK- T, B, and natural killer cell; UV- unscheduled visits; ¹¹ Study visits may be rescheduled or study procedures may be waived or modified to be performed remotely due to travel limitations or safety concerns during the coronavirus disease 2019 pandemic (as described in protocol section [6](#)); ¹² Some vital signs or assessments may not be possible if performed virtually. Visit 8 will begin after completion of procedures listed at Visit 8 in [Table 2](#). Visits 9 to 14 will be scheduled 28 days (\pm 7 days) from the prior visit. * Urine pregnancy test prior to administration of mepolizumab in women of child-bearing potential (not performed at remote visits); [#] Performed electronically via REDCap. A weekly symptom log will be completed through Visit 14; PROs will be done weekly and monthly through Visit 14.

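### Pregnancy testing is dropped at every remote de-escalation visit while dosing continues, so up to five consecutive doses can be given with no scheduled test

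*Combined protocol and SAP*

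**What the plan says.** Section 4.3 sets the general rule: "Females of childbearing-potential must have a negative pregnancy test result prior to receiving mepolizumab at each on-site study visit". Remote doses fall outside it.

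At Visit 8 (section 6.4.1) the list includes "Urine pregnancy test (females of childbearing potential only", and the 500 mg infusion is then given in the Day Hospital. From Visit 9 the rule changes with the setting. Sections 6.4.2 (Visits 9 and 10, 500 mg) and 6.4.3 (Visits 11 to 13, 300 mg) both allow a remote visit where COVID-19 restrictions or travel make it necessary. Both have the pharmacy supply autoinjectors, and both list "Pregnancy test (females of childbearing potential; not performed at a remote visit". The Table 2 footnote in Appendix B repeats this: "Urine pregnancy test prior to administration of mepolizumab in women of child-bearing potential (not performed at remote visits". Section 6.4.2 prefers in-person attendance for Visits 9 and 10 and wants Visit 10 at NIH where feasible. Section 6.4.3 states no such preference.

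Section 5.4 lets the subject or a caregiver inject, and for remote visits "subjects will either have an observed administration via telehealth or will log the dose on a dose tracker". Section 4.5 excludes pregnant women because "the effects of mepolizumab on the developing human fetus are unknown", and section 12.3 gives the first action on pregnancy as "Discontinue the study agent and procedures and withdraw from this study".

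**The concern.** The reason for testing is the unknown effect of the drug on a fetus, and that reason does not depend on where the injection is given. At Visits 4, 6, 7 and 8 every dose follows a scheduled urine test. At a remote visit the dose is still given and the test is not.

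What remains is contraception or abstinence, the woman's own report of a known or suspected pregnancy, a virtual history and the adverse event assessment. These can prevent a pregnancy or pass on a suspicion, but they do not detect a pregnancy she has not noticed. The discontinuation rule in sections 6.7, 12.3 and 12.8 acts only once pregnancy is known or suspected. At stake is repeated, avoidable dosing of an early unrecognised pregnancy. An on-site subject on the same schedule would have been tested before each of those doses. A remote dose may also be unobserved, so there may be no live contact with staff at the moment of injection.

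**Working it through.** **Inputs**
- Visit days, Appendix B Table 2: Visit 8 = 99, Visit 9 = 127, Visit 10 = 155, Visit 11 = 183, Visit 12 = 211, Visit 13 = 239, Visit 14 = 267.
- Spacing: 28 days ± 7 from the prior visit (sections 6.4.2 to 6.4.4), so each interval is 21 to 35 days.
- Doses: 500 mg at Visits 8 to 10 and 300 mg at Visits 11 to 13 (section 5.4).
- Tests: always at Visit 8; at Visits 9 to 13 only if on site.

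**The plan's own schedule reproduces.** 99 + 5 × 28 = 239 (Visit 13) and 99 + 6 × 28 = 267 (Visit 14). De-escalation doses at Visits 8 to 13 = 6.

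**Case A: Visits 9 to 13 all remote**
- Untested doses: Visits 9, 10, 11, 12 and 13 = 5.
- Drug given untested: 2 × 500 + 3 × 300 = 1900 mg.
- Last test to last dose: 239 − 99 = 140 days. With windows: 5 × 21 = 105 to 5 × 35 = 175 days.

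**Case B: Visit 10 on site, Visits 11 to 13 remote**
- Longest run of untested doses: Visits 11, 12 and 13 = 3 (Visit 9, if remote, is one further untested dose before the Visit 10 test).
- Drug given untested in that run: 3 × 300 = 900 mg.
- Last test to last dose: 239 − 155 = 84 days; upper window 3 × 35 = 105 days.

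**With a test before every dose**
- Untested doses: 0.
- Longest interval between tests while dosing: 28 days, 35 at the upper window.

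| | Longest untested run | Dose in run | Test to last dose (nominal / upper window) |
|---|---|---|---|
| A: all remote | 5 | 1900 mg | 140 / 175 days |
| B: Visit 10 on site | 3 | 900 mg | 84 / 105 days |
| Test before each dose | 0 | 0 mg | not applicable |

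**No later scheduled test closes the gap.** The Visit 14 list in section 6.4.4 has no pregnancy test. Section 6 says "blood and/or urine samples may be collected with a local specialist or healthcare provider" when a visit is remote, but assigns no pregnancy test to that route.

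**The case against.** The strongest reply is that the waiver is intentional and consistent across four places, and that contraception carries the main burden. Section 4.3 asks for complete abstinence or two methods, at least one of them a barrier, used consistently and continued for about 100 days after the last dose. A woman who suspects pregnancy must tell staff at once, which triggers discontinuation without a scheduled test. Remote visits are a fallback, so five in a row is an extreme case; three doses of 300 mg SC is more likely, and that is the approved HES dose and route. The counts are of untested doses, not of fetal exposure. Five exposed doses would need conception near Visit 8 and a pregnancy unsuspected through five monthly contacts. Section 4.3 also equates 100 days with five half-lives (about 20 days each), so drug already given would persist after a positive test.

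Much of this is fair. It makes the point a safety gap and not a contradiction, and it limits the likely frequency. It does not remove the gap. The same contraception rule binds on-site subjects, yet the protocol still tests them before each dose. Self-report cannot act on a pregnancy that is not suspected. Residual drug is a reason to avoid further doses, which is the purpose of stopping.

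**Conclusion.** The concern holds. The plan allows five consecutive doses (1900 mg over 140 days, up to 175) after the last scheduled pregnancy test in the worst case. In the more plausible case, with Visit 10 at NIH, it allows three (900 mg over 84 days, up to 105). The counts rest only on the Table 2 days, the visit windows and the section 5.4 doses.

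How many women this affects cannot be derived. The documents give neither the number of women of childbearing potential nor the expected number of remote visits. The protocol summary plans 12 subjects, section 15.1 expects 5, and only those judged to benefit enter de-escalation, so the number affected could be zero. The gap is partly mitigated and probably rare, but it is avoidable at little cost and should be closed. No endpoint, sample size or analysis is affected.

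**What to change.** Tie the test to the dose.

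1. **Section 4.3:** require a negative pregnancy test before each dose of mepolizumab, whether on site or remote.
2. **Sections 6.4.2 and 6.4.3 and the Table 2 footnote:** delete the remote-visit waiver for the pregnancy test. State that at a remote visit a negative urine test is required before injection, using a kit sent with the autoinjectors or a test at the local laboratory.
3. **Section 5.4, Tracking of Dose:** have the result and its date reported on the telehealth call, or entered on the dose tracker and confirmed by the study team, before the dose is taken.

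A positive result then follows sections 6.7 and 12.3 unchanged.

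**Cost:** at most five urine kits per woman of childbearing potential. Even if all 12 planned subjects were such women, entered de-escalation and were remote throughout, that is 12 × 5 = 60 kits. The autoinjectors are already being supplied, and the CBC has no remote waiver at these visits, so local sampling is already expected. The drawbacks are that a self-read, self-reported result is less controlled than an on-site test, and that a dose may wait briefly for confirmation.
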